To address the primary objective, we will first test for normality of the distribution of the proportion of platelet responders. If the assumption of normality is upheld, a one-sided Cochran-Mantel-Haenszel (CMH) test, at alpha=0.025, will be used to compare the proportion of platelet responders between the two arms. If the normality assumption is violated, then a one-sided Fisher's exact test will be used. The monitoring boundaries and levels of significance for the interim and final analyses of the primary endpoint are detailed in Table 16A. If a monitoring boundary is crossed in an interim analysis, an independent Data Safety Monitoring Board (DSMB) will make a non-binding recommendation regarding trial conduct or potential closure. In the final analysis, we will reject the null hypothesis if the upper (efficacy) boundary z-value of 1.99302 is crossed; in that case, it will be reasonable to conclude that the rate of platelet response is significantly greater in patients treated with eltrombopag than standard first-line treatments. Otherwise, we will conclude that there is insufficient evidence to support superiority of eltrombopag over standard first-line treatments. All randomized patients will be analyzed in the ITT analysis.

Selection of platelet measurements for the determination of platelet response.

All platelet counts will be reported, and the four measurements closest in time to Weeks 6, 8, 10, and 12 will be selected for the determination of the primary endpoint. Within a sliding one-week window, only one measurement can be selected. Patients who have <3 platelet measurements due to missing data will be classified as non-responders.

c. Analysis of Secondary Endpoints

Analyses of all secondary endpoints will be performed in the subset of evaluable patients. To determine the effects of missing data, sensitivity analyses will be performed using two approaches: a) assuming missing at random; and, b) assuming missing not at random. For each secondary endpoint, the assumption of normality will be tested. If violated for binary endpoints, a Fisher's exact test will be used. If violated for continuous endpoints, a Wilcoxon rank-sum test will be used.

To address secondary objective 3.2.1, the Cochran-Mantel-Haenszel test will be used to compare the proportion of patients with poor WHO Bleeding Score and poor Modified Buchanan Score between the two arms.

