To address secondary objective 3.2.2, an ANCOVA model will be used to compare the number of rescue therapies between the two arms.

To address secondary objective 3.2.3, the observed proportion and 95% confidence interval of platelet responders will be calculated in the subset of patients who required a rescue treatment during weeks 1-2 of the study.

To address secondary objective 3.2.4, the Cochran-Mantel-Haenszel test will be used to compare the proportion of patients who do not need ongoing treatment at 12 weeks and 6 months between the two arms.

To address secondary objective 3.2.5, the Cochran-Mantel-Haenszel test will be used to compare the proportion of patients with a treatment response at one year between the two arms.

To address secondary objective 3.2.6, an ANCOVA model will be used to compare the number of 2nd-line therapies between the two arms

To address secondary objective 3.2.7, an ANCOVA model will be used to compare the absolute change from baseline in percentage of regulatory T cells at 12 weeks and 1 year between the two arms

To address secondary objective 3.2.8, KIT scores will be calculated as per the methods described in Klaassen et al.²⁸ Spaghetti plots will be used to visualize the KIT scores over time per patient by treatment arm. An ANCOVA model will be used to compare the absolute change from baseline in KIT overall score at 1 week, 4 weeks, 12 weeks, and 1 year between the two arms. An ANCOVA model will be used to compare the Change Scale score at 1 week, 4 weeks, 12 weeks, and 1 year between the two arms.

To address secondary objective 3.2.9, fatigue scores will be calculated as per the methods described in Hockenberry et al.²⁹ All measures will be rescaled from 0 (no fatigue) to 100 (high fatigue) for consistency in scoring. Spaghetti plots will be used to visualize the fatigue scores over time per patient by treatment arm. The PROMIS tired question: “My child (I) got tired easily never to almost always” will be used as an anchor with severe fatigue defined as “often” or “almost always” with moderate fatigue being “sometimes”. An ANCOVA model will be used to compare the absolute change from baseline in fatigue at 1 week, 4 weeks, 12 weeks, and 1 year between the two arms.

To address secondary objective 3.2.10, an ANCOVA model will be used to compare iron indices at 12 weeks, 6 months, and 1 year between the two arms

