To address the survey-related aspects of exploratory objectives 3.3.3, the PROMIS® measures will be scored as according to the described approach ²². Mixed-effects model and the generalized estimating equations (GEE) allow for covariate adjustment and can model both within group effects (time) and between group effects ³⁰. The results will be summarized with adjusted means with associated 95% confidence intervals at each time point for each treatment group. For the primary analysis, these models will include the main effect of time (T0-T2). PHIS is a confidential database that allows use among the 47 member hospitals including a number of prominent pediatric hematology centers that participate in ICON. Descriptive analysis will be performed using PHIS data after patients have been identified using PHIS diagnosis codes to identify patients with ITP. Descriptive statistics will be performed to analyze financial burden measures. As instruments have not been validated, item level comparisons will be made between standard therapy and eltrombopag.

During the trial, on an ongoing basis the study team will monitor the response rate to each of the surveys. A patient will be counted as having responded to a given survey if both the baseline survey and at least one post-baseline survey are submitted. If the observed response rate for a given survey falls below 33%, the study team may consider halting the collection of that survey from subsequent patients, as it is an inappropriate use of resources, and unfair to patients, to continue to require survey submission if the survey data will be too sparse to address the study objective.

e. Interim Analysis

Interim analysis for efficacy and futility

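### KIT and fatigue are compared visit by visit with ANCOVA and no rule for missing forms, so the 1-year result can be biased if form return depends on earlier follow-up scores; one repeated-measures model would remove most of that risk.

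*Combined protocol and SAP*

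**What the plan says.** - **Schedule.** Section 9 and its visit tables collect KIT and the fatigue scales at baseline, Weeks 1, 4 and 12, and 1 year. Neither is scheduled between Week 12 and 1 year.
- **KIT (objective 3.2.8, endpoint 5.2.8).** Section 16.c: "An ANCOVA model will be used to compare the absolute change from baseline in KIT overall score". The times are given in the same sentence: "in KIT overall score at 1 week, 4 weeks, 12 weeks, and 1 year between the two arms".
- **Fatigue (3.2.9, 5.2.9).** Section 16.c: "An ANCOVA model will be used to compare the absolute change from baseline in fatigue", at the same four times.
- **Fallback.** After a normality test: "If violated for continuous endpoints, a Wilcoxon rank-sum test will be used".
- **Analysis set.** "Analyses of all secondary endpoints will be performed in the subset of evaluable patients". Evaluable means at least one dose received; it does not depend on returned forms.
- **Missing data.** For the secondary endpoints, "sensitivity analyses will be performed using two approaches", one assuming missing at random and one assuming missing not at random. Neither method is named.
- **PROMIS (exploratory, 16.d).** Mixed-effects models and GEE are named because they "can model both within group effects (time) and between group effects". The only model term listed is a main effect of time.

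**The concern.** KIT and fatigue are each measured four times after baseline, but nothing in section 16.c links a patient's visits. Without imputation, an ANCOVA at 1 year can use only patients with a 1-year form. A patient whose last form was at Week 12 then contributes nothing to that comparison, although the Week 12 score is the best available information on the missing one.

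This matters if return of the 1-year form depends on how the child was doing earlier. The trial is open label. After Week 12 there are 52 - 12 = 40 weeks with no KIT or fatigue form. During that time many of the monthly laboratory checks apply only to patients still taking eltrombopag (section 9), so contact with the site depends on arm and clinical course. Quality of life and fatigue are part of the stated rationale (section 1), and the 1-year comparison is the one most exposed.

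**Working it through.** The documents give no power figure, SD, visit correlation or missing-form rate for KIT or fatigue, so there is no stated figure to reproduce. The check is a simulation with no true arm difference.

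**Inputs from the documents:** 98 eltrombopag and 49 standard patients (section 4, informative patients); five measurement times (section 9).

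**Assumptions:** scores multivariate normal with SD 1; correlation between visits exchangeable at 0.3, 0.5 or 0.7, or autoregressive at 0.7; only 1-year forms missing; logit of the missingness probability linear in the score, with slope 1 per SD; 2,000 simulated trials per scenario.

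**Estimators of the 1-year arm difference**

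1. ANCOVA: change at 1 year on arm and baseline, in patients with a 1-year form.
2. Repeated measures: regress the 1-year score on arm, baseline and Weeks 1, 4 and 12 in patients with the form; predict for all patients; regress the predicted change on arm and baseline. When only the last visit is missing, this is the likelihood estimate with a common unstructured covariance.

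**Absolute bias in SD units, range over the four correlation structures**

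| 1-year missingness depends on | Missing, standard / eltrombopag | ANCOVA | Repeated measures |
|---|---|---|---|
| Arm only | 35% / 20% | at most 0.005 | at most 0.006 |
| Arm and baseline | 37% / 24% | at most 0.004 | at most 0.005 |
| Arm and Week 12 score, same slope | 37% / 24% | 0.03-0.07 | at most 0.007 |
| Week 12 score, standard arm only | 37% / 20% | 0.07-0.19 | at most 0.006 |
| Week 12 score, opposite directions | 28% / 29% | 0.11-0.31 | at most 0.005 |
| Unseen 1-year score, standard arm only | 37% / 20% | 0.16-0.29 | 0.12-0.26 |

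The sign of the bias follows the direction assumed for the dependence. The upper ends of the three Week 12 rows come from the autoregressive structure.

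**Effect on a two-sided 5% test.** With d = bias / empirical SE, the rejection rate under no difference is approximately P(Z > 1.96 - d) + P(Z < -1.96 - d).

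- Same slope, exchangeable 0.5: d = 0.031 / 0.183 = 0.17, rejection about 5.3%.
- Standard arm only, exchangeable 0.5: d = 0.081 / 0.182 = 0.45, about 7.3%.
- Standard arm only, autoregressive: d = 0.193 / 0.199 = 0.97, about 16%.
- Opposite directions, exchangeable 0.5: d = 0.127 / 0.178 = 0.71, about 11%.
- Opposite directions, autoregressive: d = 0.305 / 0.195 = 1.56, about 35%.

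**Precision when missingness depends on arm only.** The SE falls from 0.200 to 0.197 (exchangeable 0.3), from 0.150 to 0.143 (exchangeable 0.7) and from 0.202 to 0.186 (autoregressive). The gain is 1.5% to 8% (for example 1 - 0.186/0.202 = 0.079).

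**The case against.** The plan has real safeguards. Non-responders to eltrombopag stay on study for data collection (8.2.2.3), all assessments are required after treatment stops (section 9), and reasons for leaving the study are few (12.2). Section 16.f assumes similar early withdrawal in the two arms. Both kinds of missing-data sensitivity analysis are planned. These points lower the likely amount of missing data. They do not ensure that questionnaires come back at 1 year, and they leave the headline estimate unchanged.

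The mechanism is also assumed. Nothing in the documents shows that return will depend on earlier scores, and opposite directions by arm is an extreme case. A child whose course changes after Week 12 may be missing for reasons the Week 12 score does not capture, and the last table row shows that the proposed model then helps only in part. This stands, and it is why a missing-not-at-random analysis must remain.

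The simulated size is approximate in another way. Parent-proxy KIT starts at age 2 and the fatigue scales are in English only (9.3), so fewer than 98 and 49 patients will contribute. The Wilcoxon fallback was not simulated.

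A reader might infer from the PROMIS paragraph that the plan gives a ready and better model to a lower tier. It does not: no arm-by-time term is listed, unweighted GEE is not protected under missing at random, and the exploratory KIT and fatigue scores also get ANCOVA.

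**Conclusion.** The main KIT and fatigue analyses leave missing forms unspecified and do not use intermediate visits. If return of the 1-year form depends on the Week 12 score, a per-visit ANCOVA is biased by about 0.03-0.07 SD when the dependence is the same in both arms and by 0.07-0.31 SD when it differs, while the repeated-measures estimate stays within 0.01 SD. These sizes rest on assumed missingness of 20-37%, an assumed slope and assumed correlations.

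Three stronger readings are not supported:

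- **Unequal missingness alone biases the comparison.** It does not: at 35% against 20% the bias was essentially zero.
- **The plan says it drops patients with missing forms.** It is silent. Per-visit available-case fits are the natural reading, not a stated rule.
- **The plan expects sparse surveys.** The 33% threshold in 16.d is a contingency for halting a survey. It counts baseline plus any one later form, so it says nothing about return at 1 year or by arm.

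The change is worth making because it costs little. It concerns secondary endpoints only.

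**What to change.** In section 16.c, for 5.2.8 (KIT overall score, parent proxy) and 5.2.9 (FS-P):

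1. Make the main analysis one mixed model for repeated measures on all post-baseline visits. Fixed effects: baseline score, baseline-by-visit, randomisation strata, arm, visit and arm-by-visit. Use an unstructured covariance.
2. Pre-state the fallback covariance structure if the model does not converge.
3. Report the arm difference at Weeks 1, 4, 12 and 1 year from this model.
4. Use this model in place of the switch to Wilcoxon after a normality test.
5. Keep the missing-not-at-random sensitivity analysis and name its method, for example delta-adjusted imputation. The missing-at-random assumption then sits in the main analysis.

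The cost is SAP wording and slightly more programming. No new data or visits are needed. The one drawback is possible non-convergence, which step 2 covers.

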5.3 Exploratory Endpoints

5.3.1 Platelet-specific endpoints

- Time to response (platelets $>30 \times 10^9/L$, and at least 2-fold increase in the baseline count and absence of bleeding) (IWG definition)¹⁷
- Treatment response (platelets $>30 \times 10^9/L$, and at least 2-fold increase in the baseline count and absence of bleeding) (IWG definition) at 12 weeks
- Time to platelet count $>100 \times 10^9/L$ and absence of bleeding (IWG definition)
- Treatment response (platelet count $>100 \times 10^9/L$ and absence of bleeding) (IWG definition) at 12 weeks
- Loss of treatment response (platelet count below $30 \times 10^9/L$, or less than 2-fold increase in the baseline count or bleeding) (IWG definition) at any time during the study period after achieving response during the first 12 weeks
- Extreme thrombocytosis (platelets $>1 \times 10^{12}/L$)

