16 STATISTICAL METHODS AND CONSIDERATIONS

Overview

This is a prospective, open label, randomized, two-arm, multi-center Phase 3 trial. Enrolled patients with newly diagnosed ITP are randomized at enrollment 2:1 to the experimental treatment arm (eltrombopag) and standard treatment arm (investigator's choice of 3 standard therapies); randomization will be stratified by patient's age at enrollment and up-front treatment status, with block size of 3. Each stratum will be limited to a maximum of 27 patients. Hence, the age distribution of the final accrued cohort may not be representative of the patient population. This is appropriate in the context of this study to ensure sufficient number of patients to study treatment effects in each age group. The primary objective is to determine

whether the proportion of patients with platelet response is greater in the experimental treatment arm compared to the standard therapy arm using a one-sided Cochran-Mantel-Haenszel (CMH) test at alpha=0.025 (see section 16.b).

Intent-to-Treat and Evaluability

For the primary objective, all randomized patients will be included in an intent-to-treat (ITT) analysis. Evaluability for the secondary and exploratory objectives: In the experimental treatment arm, patients will be considered evaluable if they receive at least one dose of eltrombopag. In the standard treatment arm, patients will be considered evaluable if they receive at least one dose of one of the standard of care treatments.

Statistical Analysis

a. Baseline Demographic and Clinical Characteristics

Patient demographic and clinical characteristics at study enrollment will be summarized using descriptive statistics, including frequencies and proportions for categorical measures, and means, medians, ranges, and standard errors for continuous measures.

b. Analysis of Primary Endpoint

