To address secondary objective 3.2.11, the frequency and proportion (with 95% confidence interval) of patients with abnormal LFTs will be calculated. Adverse event rates will be coded by body system and MedDra classification term. Adverse events and serious adverse events will be tabulated by treatment group and will include the number of patients for whom the event occurred, the rate of occurrence, and the severity and relationship to study drug. If a patient experiences the same toxicity multiple times, a patient will be counted only once for a given toxicity at the maximum grade.

d. Analysis of Exploratory Objectives

Exploratory objectives are hypothesis-generating only. Any exploratory findings need to be confirmed in an independent study.

To address the platelet exploratory objectives 3.3.1, a Cochran-Mantel-Haenszel test will be used to compare the proportion of patients between treatment arms with: (1) specific platelet-defined treatment response at 12 weeks, (2) extreme thrombocytosis, and (3) loss of treatment response (in the subgroup of patients who achieved treatment response during the first 12 weeks. Cumulative incidence curves by treatment arm will be created to describe: (1) time to response and (2) time to platelet and bleeding response. Gray's test will be used to compare the cumulative incidence between treatment arms.

To address the patient-reported outcomes exploratory objectives 3.3.2, KIT scores and fatigue scores will be calculated as described. Spaghetti plots will be used to visualize the scores over time per patient by treatment arm. An ANCOVA model will be used to compare the absolute change from baseline at 1 week, 4 weeks, 12 weeks, and 1 year between the two arms.

To analyze the non-survey endpoints of exploratory objective 3.3.3, a Cochran-Mantel-Haenszel test (for categorical outcomes) or an ANCOVA model (for

continuous outcomes, like the cost of therapy) will be used to compare the two arms.

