- Power spent: the probability that the significance is found and the trial is stopped, given the alternative hypothesis (also called “exit probabilities”).
- Total power: these are the cumulative power values.

Figure 1. O’Brien-Fleming interim monitoring efficacy (red) and futility (green) boundaries for the rate of sustained of platelet response, comparing the eltrombopag arm to the standard of care arm using a two-sided Cochran-Mantel-Haenszel test

Interim analyses for safety

AEs and SAEs will also be reviewed at interim analysis 1 and 2. If any toxic deaths, or 2 intracranial hemorrhages, or 2 unprovoked thromboses are found at the first interim analysis, study will be temporarily halted to accrual for further evaluation.

f. Sample Size and Study Duration

Power Calculations for the Primary Objective

147 “informative” (as defined below) patients, randomized 2:1 to the experimental treatment arm and standard treatment arm, will be required to provide 81.4% power to detect an absolute difference of 25% in the proportion of patients who are platelet responders, assuming the response rate is 75% in the experimental treatment arm and 50% in the standard treatment arm, using a one-sided Cochran-Mantel-Haenszel (CMH) test and a type I error rate of 0.025. In order to provide at least 147 informative patients, up to 162 patients will be enrolled and randomized.

The first time point at which the primary endpoint, platelet response, will be assessed is 5 weeks after enrollment. A small number of patients, approximately

9%, are anticipated to withdraw from the study (i.e., withdraw from protocol therapy AND data submission) prior to the 5-week platelet assessment. It is reasonable to assume that the study withdrawal rate will be similar across the treatment arms. These patients are non-informative for the primary objective to assess the efficacy of eltrombopag; such patients dilute the treatment effect and as a result the power is diminished. These “non-informative” patients will be classified as non-responders and included in the ITT analysis. We will assume that 9% of randomized patients, a conservatively high estimate, will be non-informative. To account for the diluting effect the non-informative patients have on the comparison of response rates, we plan to enroll and randomize up to an additional 15 patients (~9%).

Total sample size and study duration

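### Loss of response is tested between arms only among patients who responded, a group formed after randomisation, so a difference in either direction cannot be attributed to treatment

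*Combined protocol and SAP*

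**What the plan says.** Section 5.3.1 uses the IWG definition of response: platelets above 30 ×10⁹/L, at least double the baseline count, and no bleeding. It counts loss of that response "at any time during the study period after achieving response during the first 12 weeks". Section 16.d then tests loss between arms by CMH "in the subgroup of patients who achieved treatment response during the first 12 weeks".

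The plan has no version of this endpoint that keeps every randomised or every evaluable patient. For exploratory objectives generally, section 16 sets an evaluable population: "In the experimental treatment arm, patients will be considered evaluable if they receive at least one dose of eltrombopag", with a matching rule for the standard arm. The responder restriction comes on top of that.

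Section 16.d labels this part of the plan: "Exploratory objectives are hypothesis-generating only".

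**The concern.** Randomisation makes the arms comparable as a whole. It does not make the responders in one arm comparable with the responders in the other when treatment affects who responds. If eltrombopag brings harder cases to a response, its responder group holds patients who would not have responded on standard therapy, and they may relapse more often. The CMH stratification by age and prior treatment does not repair this, because patients are still selected on outcome within each stratum.

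What is at stake is the reading of one exploratory p-value. Loss among responders can point against eltrombopag while more of its randomised patients keep a response. Equally, a difference in favour of eltrombopag would not measure its effect on durability.

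**Working it through.** **Plan's own figure.** The documents give none for this analysis: no IWG response rates and no loss rates. The only response rates are the planning values for the primary endpoint, "assuming the response rate is 75% in the experimental treatment arm and 50% in the standard treatment arm". They are used here as a proxy.

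**Inputs**
- Randomised: 108 and 54 (section 16.f).
- Response: 75% vs 50% (proxy), so 108 × 0.75 = 81 and 54 × 0.50 = 27 patients enter the test.
- Assumed: every patient who would respond on standard therapy would also respond on eltrombopag. This leaves 50% of patients who respond on either arm and 25% who respond only on eltrombopag.
- Assumed: loss is 20% in the first group on either arm and 50% in the second.
- Assumed: nominal significance at z of 1.96 or more in one direction (2.5%). Section 16.d states no level for exploratory tests.

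**Loss among responders**
- Eltrombopag: (0.50 × 0.20 + 0.25 × 0.50) / 0.75 = 0.225 / 0.75 = 30%.
- Standard: 20%.

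**Lasting response, all randomised**
- Eltrombopag: 0.75 × (1 − 0.30) = 52.5%.
- Standard: 0.50 × (1 − 0.20) = 40%.

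The same patients give opposite signs under the two analyses.

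**How often the responder test misleads here**
- SE of the difference = √(0.30 × 0.70/81 + 0.20 × 0.80/27) = 0.0923.
- Probability that the estimate points against eltrombopag: Φ(0.10/0.0923) = Φ(1.08) = 86%.
- The CMH test uses the null variance. Pooled loss = (81 × 0.30 + 27 × 0.20)/108 = 0.275, and null SE = √(0.275 × 0.725 × (1/81 + 1/27)) = 0.0992.
- Probability of nominal significance against eltrombopag: 1 − Φ((1.96 × 0.0992 − 0.10)/0.0923) = 1 − Φ(1.02) = about 15%.

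Simulation with 108 and 54 randomised patients gives the same 86% and 15%.

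**Varying the assumptions** (E = eltrombopag, S = standard)

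| Response, E vs S | Would-be control responders' loss, on E / on S | Extra responders' loss | Loss among responders, E vs S | Lasting response, E vs S | Result of responder test |
|---|---|---|---|---|---|
| 75% vs 50% | 20% / 20% | 40% | 26.7% vs 20% | 55% vs 40% | significant against E in about 9% |
| 75% vs 50% | 20% / 20% | 60% | 33.3% vs 20% | 50% vs 40% | significant against E in about 24% |
| 75% vs 50% | 30% / 30% | 60% | 40% vs 30% | 45% vs 35% | significant against E in about 14% |
| 90% vs 80% | 20% / 20% | 50% | 23.3% vs 20% | 69% vs 64% | significant against E in about 6% |
| 75% vs 50% | 20% / 40% | 50% | 30% vs 40% | 52.5% vs 30% | estimate against E in about 18% |
| 75% vs 50% | 20% / 50% | 50% | 30% vs 50% | 52.5% vs 25% | estimate against E in about 3% |
| 75% vs 50% | 20% / 60% | 50% | 30% vs 60% | 52.5% vs 20% | estimate against E in about 0.3% |

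In the last three rows the sign is right but the selection remains. With control loss at 40%, patients who would respond on either arm differ by 40 − 20 = 20 points, and the responder comparison shows 40 − 30 = 10.

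**The case against.** - **The rates belong to another endpoint.** This stands. The 75% and 50% refer to sustained counts above 50 ×10⁹/L in weeks 6 to 12 without rescue. The IWG response has a lower bar and need only be reached at some time in the first 12 weeks, so the arms may lie closer together and the effect may be smaller, as in the 90% vs 80% row.
- **The direction may be the opposite.** This also stands. Section 1 describes the standard agents as short-acting, with counts falling again within days or weeks in active disease, and section 8.2.1 gives them as a single dose or a four-day course. A reader might infer that the test is biased against eltrombopag, or that it penalises the better arm. The documents do not support that: it needs low loss in control responders, which section 1 makes doubtful.
- **The 15% depends on the form of the test.** With a continuity correction it is about 9%.
- **The analysis is exploratory, and lasting benefit is examined elsewhere.** True. The primary endpoint, the need for ongoing treatment at 12 weeks and 6 months, and the 1-year outcomes are not restricted to responders. This limits the importance, but none of them measures an IWG response that is kept. The hypothesis-generating label does not remove selection bias, and a confirmatory study using the same subgroup would repeat it.

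**Conclusion.** The concern holds as a minor one. Section 16.d specifies a between-arm test in a group selected by an outcome that the trial expects to differ between arms, and no all-patient version exists. A difference in either direction cannot be attributed to treatment.

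The size is unknown. The 30% vs 20% example, with lasting response of 52.5% vs 40%, shows that a reversal is possible. It rests on proxy response rates, on assumed loss rates, and on every control responder also being an eltrombopag responder. It is not a forecast: the reversal shrinks as response rates converge and disappears when control responders lose response more often. The primary analysis is not affected.

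**What to change.** In sections 5.3.1 and 16.d:

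1. Make the between-arm CMH comparison a binary endpoint: IWG response in the first 12 weeks and not lost, with non-response counted as failure.
2. Apply it to all randomised patients, or to the evaluable set that section 16 defines for exploratory objectives, and state which.
3. Judge loss only from platelet counts at visits scheduled in both arms. After week 12, the section 9 schedule restricts most monthly counts to eltrombopag patients still on drug, so loss is more likely to be detected in that arm. Without this limit, the new endpoint would remove the selection bias but keep unequal detection.
4. Report loss among responders by arm descriptively, without a p-value.

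The cost is wording only; the data are already collected. The small downside is that losses seen only at eltrombopag-only or unscheduled visits do not count in the comparison. They can still appear in the descriptive table.
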